## **Randomization**

The patients were randomly assigned to the CO2 group and O2 group at a 1:1 ratio. 52 opaque envelopes were made according to a random table generated by the PLAN process of SAS (SAS9.4, SAS Institute Inc). Each patient would receive an envelope which was opened by operators in surgery, when the structures of targeted segment were successfully dissected and anesthesiologist was about to re-expand the collapsed lung.

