## **Surgical Procedures:**

Before anesthesia induction, anesthesiologist placed the electrocardiogram, non-invasive blood pressure, pulse oximetry, bispectral index (BIS) monitor and completed radial artery catheterization successively. All patients were given general anesthesia with double lumen endotracheal intubation. After patients were placed in lateral decubitus position, one-lung ventilation of the dependent lung was initiated with 1.0 of FiO2 (fraction of inspiration) and 5 cm H2O of positive end-expiratory pressure. All patients underwent single-port thoracoscopic surgeries which were performed by the same surgical and anesthesia team. The surgical incision was about 3 cm long and located on the fourth or fifth intercostal space of the midaxillary line.

With the guidance of 3D reconstruction, the targeted segmental bronchi and vessels could be precisely identified and dissected, after that ISP was identified by modified inflation-deflation method. Firstly, anesthesia used fiberoptic bronchoscope to confirm the position and patency of endotracheal tube, suction if necessary. Then the non-dependent lung was re-expanded with airway pressure no more than 20 cm H2O and the flow of gas at 8 L/min, while the dependent ventilated lung was kept on mechanical ventilation without change. The non-dependent lung was re-expanded by pure O2 in O2 group, or by CO2 in CO2 group which was obtained from CO2 insufflator.

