## Outcome Measures

**Primary outcome:** The intersegmental border appearance time during the surgery.

**Secondary outcome:** Including BIS, arterial blood gases, arterial pressure and heart rate obtained when the patient was breathing room air (RA), the non-dependent lung was ready to be re-expanded when the bronchi and vessels of targeted segment had been dissected (0min), 3, 5, and 15 min after the non-dependent lung was fully inflated. Besides that, end-tidal carbon dioxide partial pressure (PetCO2) at 0, 3, 5, 15 min, duration of surgery, duration of drainage, total drainage, postoperative hospital stay, global Quality of Recovery 40 questionnaire (QoR-40) at 48 hours and 1 week after operation, postoperative complications (such as air leakage, pneumonia, atrial fibrillation, and all the postoperative complications were classified by the Clavien-Dindo classification of adverse events) were also included as secondary outcomes.

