## **Statistical analysis**

The demographic and baseline characteristics of the patients, vital signs, TISP, arterial blood gas indexes, and the perioperative outcomes could be divided into two types: categorical variables and continuous variables. The categorical variables were expressed by frequencies and proportions, and were analyzed by chi-square test or continuity correction chi-square test. The continuous variables were expressed by mean  $\pm$  SD, and were analyzed by t test or Fisher's exact test. All statistical analyses were 2 sided, and  $p < 0.05$  was considered statistically significant. Statistical analyses were performed by SPSS (IBM SPSS 28.0, SPSS Inc).

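### The operators learn the gas just before the lung is re-expanded, so if they are the ones who call the intersegmental border, the primary endpoint is read unmasked

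*Combined protocol and SAP*

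**What the plan says.** The Study Protocol section declares the trial open-label. Under Randomization, "Each patient would receive an envelope which was opened by operators in surgery", and the moment is given as "when the structures of targeted segment were successfully dissected and anesthesiologist was about to re-expand the collapsed lung". The section describes the envelopes as opaque, 52 in number, with 1:1 allocation; it mentions no numbering, sealing or log.

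Under Surgical Procedures, dissection comes first, and "after that ISP was identified by modified inflation-deflation method". That sentence is passive and names no reader. The operations were all single-port procedures "which were performed by the same surgical and anesthesia team". The lung is re-expanded with pure O2 "or by CO2 in CO2 group which was obtained from CO2 insufflator", at "airway pressure no more than 20 cm H2O and the flow of gas at 8 L/min".

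Under Outcome Measures, the primary outcome is "The intersegmental border appearance time during the surgery", and nothing more is said about it. Under Statistical analysis, the abbreviation TISP appears among the variables without a definition. Continuous variables are summarised by mean and SD "and were analyzed by t test".

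**The concern.** The primary endpoint appears to be a visual judgement of when a border has emerged. A reader who knows the gas, and expects one gas to work faster, may call the border earlier or later in that arm without meaning to. Randomization and concealment decide fairly who gets which gas, but they do not protect a reading made afterwards. The pressure ceiling and flow rate standardise delivery, not the reading. No written criterion for appearance limits the reader's discretion.

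At stake is the one comparison that the trial exists to make. A reading shift between arms would look exactly like a gas effect. The exposure also looks avoidable, because the documents describe no step for which the operators need the allocation.

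**Working it through.** The plan states no effect size, SD or power, so it has no figure of its own to reproduce. The check is mainly one of sequence, with an illustration added.

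**1. Order of events.** From Randomization and Surgical Procedures: segment dissected; envelope opened by the operators; lung re-expanded with the allocated gas; intersegmental plane identified. The border can appear only after re-expansion, so knowledge of the arm comes before the primary event in every patient.

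**2. Who reads the border.** No section names an assessor, a clock start, an end criterion, a masked or second reader, or a video recording. The 0 min point under Outcome Measures belongs to the secondary measurements, and the 3, 5 and 15 min points run from full inflation. Neither is stated to be the clock start for the primary outcome. That the operators call the border is a likely inference, because one team does every case and no one else is named.

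**3. Who needs the allocation.** The gas is given through the airway, and the anesthesiologist, who re-expands the lung, is already present when the envelope is opened.

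**4. Illustration of a reading shift.** Inputs: 52 envelopes at 1:1, taken as n = 26 per arm (exact balance is assumed); two-sided 0.05; t test with 26 + 26 − 2 = 50 df, critical value 2.0086. Let *b* be an assumed systematic difference in reading between arms, in SD units, with no true gas effect. The noncentrality is b / √(2/26) = b / 0.2774, and the rejection rate is the area of the noncentral t beyond ±2.0086.

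| Assumed shift *b* | Noncentrality | False-positive rate |
|---|---|---|
| 0 | 0 | 5.0% |
| 0.10 SD | 0.36 | 6.4% |
| 0.25 SD | 0.90 | 14.3% |
| 0.50 SD | 1.80 | 42.4% |

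**5. Imperfect masking.** If masking fails in a fraction *f* of patients, the mean shift is f × b. With b = 0.50 SD, f = 20%, 40%, 60% and 80% give mean shifts of 0.10, 0.20, 0.30 and 0.40 SD, and rates of 6.4%, 10.9%, 18.6% and 29.3%. Applying the shift patient by patient in simulation (200,000 trials each) gave 6.4%, 10.6%, 18.2% and 28.8%. Partial masking still helps, but less the more often it fails.

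**6. A large true effect.** With a true difference of 1.5 SD and an opposing shift of 0.50 SD, the net difference is 1.0 SD, the noncentrality is 1.0 / 0.2774 = 3.61, and power is 94.2%. The test would usually still reject, but the estimated time difference would be wrong by the full 0.50 SD.

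**The case against.** The trial says openly that it is open-label, and late opening of the envelope is good practice. Both are true. Disclosure does not reduce the risk, however, and late opening protects the dissection, not a reading made after it.

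The operators may not be the readers. This stands as a limit on the point. A reader might infer that the plan has the operators time the border; the documents do not say so.

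Masking may not work well. The CO2 comes from an insufflator that may be in view, PetCO2 is recorded at 0, 3, 5 and 15 min, and one team does every case and may learn to recognise the gas. The documents do not say who sets up the insufflator, so the absence of any step needing the allocation is partly an argument from silence. All of this stands: masking should be expected to be partial.

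If the envelope is opened away from the operators, they no longer witness the assignment. That is a real cost, and a numbered log is needed to offset it.

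The text is in the past tense, which suggests without proving that the operations are done. If so, only the reporting part of the fix remains available.

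**Conclusion.** The point holds in conditional form: the operators know the gas before the border can appear, and if they call it, the primary endpoint is open to arm-dependent reading that the planned analysis can neither detect nor remove. The change is worth making because it is cheap and the endpoint is the only primary one. Confidence is medium, because the identity of the reader is inferred and the success of masking is uncertain.

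The size and direction of any bias are unknown. The illustrative rates rest entirely on assumed shifts, assumed failure fractions and assumed equal arms, and the recommendation does not depend on them. A reader might infer that the primary result is biased, or that 42.4% estimates this trial's error rate; nothing in the documents supports either. Nor do they support reading the late opening as a flaw in allocation concealment. It keeps the allocation from influencing the dissection and should stay.

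**What to change.** Amend the Randomization section:

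- Keep the opening after dissection, but have the anesthesiologist open a sealed, sequentially numbered envelope and log its number and the time.
- Do not tell the operators the gas until the border has been called, and screen the gas source from their view where practicable.
- Make the allocation available at once for any clinical need, and record any unmasking before the call.

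Amend Outcome Measures to name the assessor and to give one start event and one end criterion, written beforehand and used in both arms. The sponsor should choose and state the start event: timing from the start of gas flow includes inflation time and timing from full inflation does not, so they are different endpoints. Replace the bare open-label description with a statement of who was masked and until when.

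Cost: no added patients, visits, procedures or staff, but some room set-up. Masking will be imperfect, since the anesthesia team knows the arm and the operators may recognise the gas. The operators also cease to witness the opening, which the numbered log offsets.

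If the operations are already complete, report who called the border, by what criterion and whether they knew the gas, and state the risk of detection bias as a limitation of the primary result. That costs about one paragraph.

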## **Surgical Procedures:**

Before anesthesia induction, anesthesiologist placed the electrocardiogram, non-invasive blood pressure, pulse oximetry, bispectral index (BIS) monitor and completed radial artery catheterization successively. All patients were given general anesthesia with double lumen endotracheal intubation. After patients were placed in lateral decubitus position, one-lung ventilation of the dependent lung was initiated with 1.0 of FiO2 (fraction of inspiration) and 5 cm H2O of positive end-expiratory pressure. All patients underwent single-port thoracoscopic surgeries which were performed by the same surgical and anesthesia team. The surgical incision was about 3 cm long and located on the fourth or fifth intercostal space of the midaxillary line.

With the guidance of 3D reconstruction, the targeted segmental bronchi and vessels could be precisely identified and dissected, after that ISP was identified by modified inflation-deflation method. Firstly, anesthesia used fiberoptic bronchoscope to confirm the position and patency of endotracheal tube, suction if necessary. Then the non-dependent lung was re-expanded with airway pressure no more than 20 cm H2O and the flow of gas at 8 L/min, while the dependent ventilated lung was kept on mechanical ventilation without change. The non-dependent lung was re-expanded by pure O2 in O2 group, or by CO2 in CO2 group which was obtained from CO2 insufflator.

## Outcome Measures

**Primary outcome:** The intersegmental border appearance time during the surgery.

**Secondary outcome:** Including BIS, arterial blood gases, arterial pressure and heart rate obtained when the patient was breathing room air (RA), the non-dependent lung was ready to be re-expanded when the bronchi and vessels of targeted segment had been dissected (0min), 3, 5, and 15 min after the non-dependent lung was fully inflated. Besides that, end-tidal carbon dioxide partial pressure (PetCO2) at 0, 3, 5, 15 min, duration of surgery, duration of drainage, total drainage, postoperative hospital stay, global Quality of Recovery 40 questionnaire (QoR-40) at 48 hours and 1 week after operation, postoperative complications (such as air leakage, pneumonia, atrial fibrillation, and all the postoperative complications were classified by the Clavien-Dindo classification of adverse events) were also included as secondary outcomes.

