### **Exclusion Criteria:**

1. Patients who are at risk for general anesthesia.
2. Patients with serious mental illness.
3. Pregnancy or lactating women.
4. Active bacterial or fungal infections.
5. Patients with Interstitial pneumonia, pulmonary fibrosis or severe emphysema.
6. Conversion to thoracotomy in surgery.
7. Preoperative assessment of patients undergoing lobectomy.

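### The pre-gas 0-min values of BIS, blood gases, arterial pressure, heart rate and PetCO2 are not used as a baseline in the arm comparison, which costs precision in these secondary outcomes

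*Combined protocol and SAP*

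**What the plan says.** **Timing.** Outcome Measures lists BIS, arterial blood gases, arterial pressure and heart rate on room air, when the operated lung is ready for re-expansion, and later: "0min), 3, 5, and 15 min after the non-dependent lung was fully inflated". It adds "end-tidal carbon dioxide partial pressure (PetCO 2 ) at 0, 3, 5, 15 min". Under Surgical Procedures the two arms differ only from re-expansion onward: "The non-dependent lung was re-expanded by pure O2 in O2 group, or by CO2 in CO2 group". The 0-min value therefore comes before the study gas for all five measures.

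**Analysis.** Statistical analysis summarises continuous variables by mean and SD, "and were analyzed by t test or Fisher's exact test". Fisher's exact test does not suit a continuous variable, so the t test is what remains. Each two-sided p below 0.05 "was considered statistically significant". The section names no covariate, change score, repeated-measures model, main time or multiplicity rule.

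**Allocation.** Randomization says "52 opaque envelopes were made according to a random table", at 1:1, and that the envelope is opened "when the structures of targeted segment were successfully dissected and anesthesiologist was about to re-expand the collapsed lung". This is the same stage of surgery as the 0-min reading; which comes first is not stated.

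**The concern.** A value taken just before the study gas is the natural baseline for the effect of that gas. Patients differ at 0 min for reasons unrelated to allocation. If the later values carry those differences forward, an unadjusted comparison leaves them in the error term. With about 26 patients per arm that matters: the trial's evidence on gas exchange, circulation and BIS under CO2 inflation comes from these variables, and a wide interval says little either way.

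A between-arm test at 0 min, which the wording seems to allow, would answer no question about the gas, because none has been given.

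A secondary point is that each variable has three post-gas times and no stated order of importance, so it has three chances of a p value below 0.05.

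**Working it through.** The documents give no power, effect size or SD, so there is no stated figure to reproduce. Everything below is in SD units of the later value.

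**Inputs**
- Two-sided 5% level (Statistical analysis).
- 52 envelopes at 1:1 (Randomization), taken as n = 26 per arm. The number could be lower, since Exclusion Criteria includes "Conversion to thoracotomy in surgery"; 24 per arm is shown as well.
- 80% power (assumed).
- Correlation ρ between the 0-min and the later value: not in the documents, so assumed as 0.3, 0.5, 0.7 or 0.8, with 0 as the worst case.

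**Step 1: unadjusted t test.** The standard error is √(2/26) = 0.277 SD. With 50 degrees of freedom and the noncentral t distribution, the difference detectable with 80% power is 0.792 SD. The normal approximation, 0.277 × (1.960 + 0.842) = 0.777, is close.

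**Step 2: adjusted for the 0-min value.** The variance of the arm difference is multiplied by (1 − ρ²) × (1 + 1/48). The second factor, 1.021, is the average cost of estimating the slope. The test has 49 degrees of freedom.

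| ρ (assumed) | 1 − ρ² | × 1.021 | Detectable, 26 per arm | Detectable, 24 per arm |
|---|---|---|---|---|
| t test | – | 1 | 0.79 | 0.83 |
| 0 | 1 | 1.021 | 0.80 | 0.84 |
| 0.3 | 0.91 | 0.929 | 0.76 | 0.80 |
| 0.5 | 0.75 | 0.766 | 0.69 | 0.72 |
| 0.7 | 0.51 | 0.521 | 0.57 | 0.60 |
| 0.8 | 0.36 | 0.367 | 0.48 | 0.50 |

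Adjustment breaks even at ρ of about 0.15. Below that it loses at most about 0.01 SD.

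**Step 3: why a covariate and not a change score.** Change from 0 min has variance ratio 2(1 − ρ): 1.40 at ρ = 0.3, 1.00 at 0.5 and 0.60 at 0.7. It is worse than the plain t test when ρ is below 0.5, and worse than the covariate throughout this range.

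**Step 4: three tests per variable.** With no effect and independent times, the chance of at least one p < 0.05 is 1 − 0.95³ = 14.3%. Simulating three t tests with 26 per arm and correlation 0.5, 0.7 or 0.9 between times (assumed) gives about 12.5%, 11% or 8.5%.

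**The case against.** The best defence is that nothing here is invalid. The t test is unbiased and holds 5% at any single time, the outcomes are secondary, and the gain depends on a correlation that the documents do not give. It may be low for some variables: the 0-min value is taken under one-lung ventilation, and the later ones after the other lung has been inflated. At ρ = 0.3 the gain is only from 0.79 to 0.76 SD. All of this stands and is why the point is minor. It does not remove the point, because the values are already planned and the worst-case loss is about 0.01 SD.

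It can also be said that 3, 5 and 15 min form a descriptive time course on which no success claim rests. That is fair; labelling the times exploratory would be a sufficient answer to the three-test point.

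Three stronger readings are tempting, and the documents do not support them.
- *A reader might infer that the 0-min value is not used at all.* It is listed among the outcome times, so it would be summarised and apparently tested. What is missing is its use as a baseline.
- *A reader might infer that one time, such as 3 min because it comes first, should be the main one.* Nothing in the documents says when the effect is largest or matters most. In simulations with 0-min adjustment (assumed ρ 0.3, correlation between times 0.7), the 3-min contrast had power 0.83 against 0.77 for the joint 3-df test when the effect was 0.792 SD at all times. It had only 0.31 against 0.69 when the effect peaked at 5 min (0.40, 0.792, 0.40 SD).
- *A reader might infer that opening the envelope near 0 min in an open-label trial biases the baseline.* The order is unstated, but no gas has yet been given, and the documents show no route by which knowledge of the arm would materially shift these readings.

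**Conclusion.** The point holds as a loss of precision in secondary outcomes. A pre-gas value is planned for all five measures, and the analysis section does not use it as a baseline. At 26 per arm, adjustment lowers the detectable difference by between 0.03 SD (ρ = 0.3) and 0.31 SD (ρ = 0.8). These are scenarios under assumed correlations, not estimates, and 26 per arm assumes exact balance and no loss.

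The per-variable chance of a false positive over three tests, about 8% to 14%, is a secondary matter. The primary outcome, the time to appearance of the intersegmental border, is not touched. Severity: minor.

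**What to change.** - For each of the five measures, analyse the 3, 5 and 15 min values with the 0-min value as covariate: either ANCOVA at each time, or one mixed model with arm, time, arm-by-time, 0-min value and 0-min-by-time. With complete data both give the same adjusted difference at each time.
- Report that difference with its 95% CI at all three times.
- Present room-air values (not planned for PetCO2) and 0-min values by arm descriptively, without between-arm tests.
- Either base one test per variable on a contrast that the investigators justify, for example the joint 3-df test, or state that all three times are exploratory estimates with CIs. No particular time is recommended here. One test per variable holds 5% for that variable, not across variables, so the results remain secondary.
- If data are already collected, as the past tense and the June 2023 date may suggest, label the adjusted analysis post hoc and report whether the 0-min value was recorded before the envelope was opened.

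The cost is one degree of freedom (about 2% in variance), a little analysis work and a few sentences in the plan. No new measurement is needed.

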# **Application of Carbon Dioxide for Identifying the Intersegmental Plane in Thoracoscopic Segmentectomy: A Randomized Controlled Study**

**Registration number: NCT05350137**

**Date: June 15, 2023**

## **Study Protocol**

This study was a prospective, single-center, open-label, randomized controlled trial.

This study was registered at ClinicalTrials.gov (NCT05350137), and has received the stamp of approval from the ethics committee of Tongji Hospital, Tongji Medical College, Huazhong University of Science and Technology (NO: TJ-IRB20220140). All enrolled patients signed the informed consent form.

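### Duration of surgery has no stated start or stop; read as the whole operation, it includes time before allocation that costs precision and carries no information about the gas

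*Combined protocol and SAP*

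**What the plan says.** Outcome Measures lists among the secondary outcomes "duration of surgery, duration of drainage, total drainage, postoperative hospital stay". It does not say when the operating clock starts or stops.

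Under Randomization, patients are "randomly assigned to the CO2 group and O2 group at a 1:1 ratio", and "52 opaque envelopes were made according to a random table". Each envelope is "opened by operators in surgery, when the structures of targeted segment were successfully dissected and anesthesiologist was about to re-expand the collapsed lung". Surgical Procedures gives the same order of steps: "the targeted segmental bronchi and vessels could be precisely identified and dissected, after that ISP was identified by modified inflation-deflation method". The stated difference between the arms comes after that: "The non-dependent lung was re-expanded by pure O2 in O2 group, or by CO2 in CO2 group".

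Statistical analysis assigns continuous variables to a t test at the two-sided 0.05 level and names no covariate. No section gives the length or SD of the operation, or of the parts before and after the envelope is opened.

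**The concern.** Allocating late is a sound choice, and the primary outcome fits it, because the border can appear only after the gas is given. Operating time has not been aligned in the same way. On its ordinary reading it is the sum of a part that is finished before the arm is known and a part that follows. Only the second can respond to CO2 or O2.

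The first part has the same expected value in both arms, but it varies from patient to patient. That variation enters the standard error of the comparison and brings no information about the gas. What is at stake is how well the trial can say whether a faster border shortens the operation. With about 26 patients per arm there is little precision to spare.

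**Working it through.** **Inputs from the documents.** 52 envelopes at 1:1, so 26 per arm (Randomization). Two-sided 0.05 and an unadjusted t test (Statistical analysis). The 52 cannot be reproduced, because no effect size, SD or power accompanies it.

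**Assumptions.** The documents give no SD. I take a total-duration SD of 40 min and independent phases. I vary the share *s* of the total variance that arises before allocation.

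**Structure.** Total = pre + post, and the gas can change only post. With randomised allocation the expected difference in pre is zero, so total and post have the same expected difference between arms. They differ in variance: Var(total) = Var(pre) + Var(post) + 2·Cov(pre, post). With independent phases, SD(post) = SD(total) × √(1 − s).

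**Precision.**
- SE of the difference = SD × √(2/26) = 0.277 × SD.
- 95% half-width = t(50 df) × SE = 2.009 × 0.277 × SD = 0.557 × SD.
- Difference detectable with 80% power = 0.792 × SD.
- Equivalent sample-size factor = 1/(1 − s).

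| Pre-allocation share of variance | SD used (min) | 95% half-width (min) | Detectable, 80% power (min) | Equivalent sample size |
|---|---|---|---|---|
| Total duration, unadjusted | 40.0 | 22.3 | 31.7 | 1 |
| 10% | 37.9 | 21.1 | 30.1 | 1.1 times |
| 25% | 34.6 | 19.3 | 27.4 | 1.3 times |
| 50% | 28.3 | 15.8 | 22.4 | 2 times |
| 75% | 20.0 | 11.1 | 15.8 | 4 times |

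The last four rows time from envelope opening. The factors restate the assumed shares; they are not evidence about this trial.

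**Check on bias and error rate.** In 20,000 simulated trials with 26 per arm, independent phases and SD(pre) twice SD(post), type I error was 0.051 for post-allocation time and 0.049 for total duration. With a true effect of 0.8 SD(post), the mean estimated difference was 0.80 for both. Power was 0.81 for post-allocation time and 0.24 for total duration. The defect is lost precision and nothing else.

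**Effect of correlation.** For the same 0.8 SD effect with SD(pre) equal to SD(post), power by normal approximation is 82% timed from the envelope. Over the whole operation it is 53% with independent phases and 43% with correlation 0.3. A strongly negative correlation would reverse the advantage of simple post-allocation timing, when the correlation is below −SD(pre)/(2 × SD(post)). Nothing in the documents points to that.

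**The adjusted alternative.** Because total − pre = post, a linear model with arm and pre as terms gives the same arm coefficient whether total or post is the response. Adjusting total duration for incision-to-envelope time therefore removes the same noise at the cost of one degree of freedom, and it copes with correlation of either sign.

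**The case against.** Total operating time is a conventional outcome, and its comparison here is valid: unbiased, with the correct error rate. A chance imbalance in dissection time that looked like a saving would be part of the ordinary 5% error and not an extra flaw. This is one secondary outcome among many. All of that stands, and it limits the point to precision.

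The remedy may also not make the question answerable. No expected saving is stated. If it were 5 to 10 min (an assumption), power with SD 40 min is about 7 to 14%. Timing from the envelope raises it to about 10 to 24% at a 50% share and 14 to 42% at 75%. That is an improvement, but the outcome stays underpowered for savings of that size. The confidence interval would still be narrower.

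Three stronger readings are tempting and should be resisted:
- A reader might infer that the plan states that the clock runs over the whole operation. It gives no definition; the whole operation is only the ordinary meaning of the term.
- A reader might infer that most of the operation precedes allocation. No timing data support this, and share of duration is the wrong quantity, because precision depends on share of variance.
- A reader might look only at the 50% and 75% rows and conclude that the trial forgoes a doubling or quadrupling of its sample size. At 10% the gain is hardly visible, and the documents do not say which row applies.

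**Conclusion.** The point holds as a cheap improvement in precision. It follows from the documents that the envelope is opened after dissection, that the arms differ in the re-expansion gas, that operating time has no defined start or stop, and that no adjustment is planned. On the ordinary reading, pre-allocation time enters the comparison as noise.

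The size cannot be determined from the documents. Under the stated assumptions (SD 40 min, independent phases, 26 per arm), the half-width falls by between about 1 min at a 10% share and about 11 min at a 75% share. There is no bias, no inflation of type I error and no effect on the primary outcome. If the sponsor meant something other than the whole operation, the missing definition still needs to be supplied, and the same edit supplies it.

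**What to change.** 1. Define the start and stop of the operating-time outcome.
2. Record the clock time at which the envelope is opened. Compare the arms on time from envelope opening to end of surgery, or on total duration in a linear model adjusted for incision-to-envelope time. Specify one of the two in advance.
3. Start the clock at envelope opening, not at the start of gas delivery. Surgical Procedures places a bronchoscopic check, with suction if needed, before re-expansion, and CO2 comes from an insufflator. A clock started at gas delivery would leave out any set-up time that follows allocation and could differ by arm.
4. Still report total duration by arm, and report incision-to-envelope time by arm as a pre-randomisation characteristic, so that any chance imbalance can be seen.

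The cost is one extra clock time, close to the 0 min point at which the plan already takes measurements. If envelope opening was not timed, the recorded 0 min is a close substitute. No extra patients or procedures are needed. The envelope-to-end interval is a less conventional outcome and harder to set beside other series; the adjusted analysis of total duration avoids that.

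### QoR-40 is listed only after surgery and compared by a raw t test; a preoperative score with ANCOVA could cheaply add precision to this secondary outcome

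*Combined protocol and SAP*

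**What the plan says.** Outcome Measures names one primary outcome, "The intersegmental border appearance time during the surgery", and a long list of secondary outcomes. Among the latter is the "global Quality of Recovery 40 questionnaire (QoR-40) at 48 hours and 1 week after operation". No preoperative administration is mentioned. BIS, blood gases, arterial pressure and heart rate, by contrast, each have a room-air reading and a reading just before re-expansion.

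Statistical analysis says that continuous variables are summarised by mean and SD "and were analyzed by t test or Fisher's exact test". No covariate-adjusted model appears anywhere. Baseline characteristics are mentioned ("The demographic and baseline characteristics of the patients, vital signs, TISP") but not itemised, and there is no schedule of assessments.

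Randomization states that "52 opaque envelopes were made according to a random table", that patients were "randomly assigned to the CO2 group and O2 group at a 1:1 ratio", and that the envelope is opened during the operation.

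**The concern.** A recovery score after surgery reflects the operation and also the patient's state beforehand. Inclusion Criteria admit patients with small ground-glass nodules, patients unfit for lobectomy and patients with metastatic disease, so preoperative status may well vary. Without a preoperative score, that variation stays in the error term of the t test at 48 hours and 1 week. Any chance difference between the arms in preoperative QoR-40 can be neither seen nor adjusted for.

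At stake is the width of the confidence interval for one secondary outcome, the only patient-reported one listed. A preoperative questionnaire needs no extra procedure.

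**Working it through.** The documents give no power, target difference or SD for QoR-40, so there is no stated figure to reproduce. Results are in SD units.

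**Inputs from the documents**
- 52 envelopes at 1:1 (Randomization), taken as n = 26 per arm, all completing the questionnaire.
- Two-sided test at 0.05 (Statistical analysis).

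**Assumptions**
- Correlation ρ between preoperative and postoperative score: 0.1 to 0.6.
- True difference: 0.6 SD, with 0.3 and 0.2 SD as smaller alternatives.

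**Step 1: raw t test.** The SE of the difference is √(2/26) = 0.277 SD, on 50 df. From the noncentral t distribution, power at 0.6 SD is 56%, and 80% power needs a difference of 0.79 SD.

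**Step 2: ANCOVA.** Relative to the raw comparison, the variance is multiplied by (1 − ρ²) × (1 + 1/(N − 4)). With N = 52 the second term is 49/48 = 1.021, the cost of estimating the slope. The residual df are 49. For example, at ρ = 0.3 the factor is 0.91 × 1.021 = 0.929. The equivalent number of patients is 52 divided by the factor.

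| Assumed ρ | Variance factor | 95% CI width vs raw | Equivalent patients (actual 52) | Power at 0.6 SD (raw 56%) |
|---|---|---|---|---|
| 0.1 | 1.011 | 1.006 | 51.5 | 56% |
| 0.2 | 0.980 | 0.990 | 53.1 | 57% |
| 0.3 | 0.929 | 0.964 | 56.0 | 60% |
| 0.4 | 0.857 | 0.926 | 60.6 | 63% |
| 0.5 | 0.766 | 0.875 | 67.9 | 68% |
| 0.6 | 0.653 | 0.809 | 79.6 | 75% |

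**Step 3: break-even.** Setting (1 − ρ²) × 49/48 = 1 gives ρ² = 1/49, so ρ = 0.14. Below that, adjustment costs slightly more than it returns.

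**Step 4: smaller effects.** At a true 0.3 SD, power goes from 18.6% to 19.6% (ρ = 0.3) or 25.9% (ρ = 0.6). At 0.2 SD it goes from 10.9% to 11.4% or 14.1%. The comparison stays underpowered either way.

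**Step 5: chance imbalance is not a second loss.** The difference in mean preoperative score between arms has SE 0.277 SD. It carries ρ × 0.277 into the follow-up difference: 0.08 SD at ρ = 0.3 and 0.17 SD at ρ = 0.6. Squared, this is ρ² × 2/26, which is exactly the share of variance that the (1 − ρ²) term removes. It is the same loss in other units.

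**Step 6: change scores.** A t test on change has variance factor 2(1 − ρ): 1.4 at ρ = 0.3, 1.0 at 0.5 and 0.8 at 0.6. It is worse than no adjustment below 0.5, and worse than ANCOVA throughout this range.

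**The case against.** A reader might infer that the recovery result is biased, because a chance difference in preoperative state passes into it. The documents do not support that. Allocation is random, and the t test's standard error and type I error already allow for chance imbalance (step 5). Nor is all preoperative imbalance hidden: the plan does summarise and compare baseline characteristics. What stays unseen is imbalance in QoR-40 itself.

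A reader might also infer, from the room-air readings of blood gases and vital signs, that the plan treats QoR-40 inconsistently. Those readings belong to a perioperative time course, and the plan does not use them as covariates either. The contrast proves little.

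The benefit cannot be sized from the documents. The correlation, its use at both 48 hours and 1 week, and the 0.6 SD difference are all assumptions. The arms differ only in the gas used to re-expand one lung, and nothing says what QoR-40 difference is expected days later. This stands, which is why the range runs down to correlations where the gain vanishes.

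Finally, the protocol is short, so an unlisted preoperative QoR-40 cannot be strictly excluded. It is also dated June 2023 and written in the past tense, so recruitment may be over. The first possibility has no support in the text. The second limits the remedy but does not change what the plan omits.

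**Conclusion.** The point holds as a low-priority improvement to one secondary outcome. As written, QoR-40 has no preoperative value and the comparison is unadjusted, so any precision available from the preoperative score is lost. The raw comparison remains valid and the primary outcome is unaffected.

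With 26 complete patients per arm, adjustment gains nothing below a correlation of about 0.14 and is worth about 1 extra patient at 0.2 and 4 at 0.3. The gain is material from about 0.4 (about 9 extra patients), rising to about 28 at 0.6. The rise in power from 56% to about 60-75% depends on both an assumed 0.6 SD difference and correlations of 0.3-0.6; it should not be read as a gain that the documents establish.

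**What to change.** Add one QoR-40 at the preoperative assessment. The envelope is opened during surgery, so the score would necessarily precede disclosure of allocation.

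The questionnaire alone is not enough. Prespecify ANCOVA of the 48-hour and 1-week scores with the preoperative score as covariate, and report the adjusted difference with a 95% CI at each time. Do not substitute a t test on change from baseline. If a preoperative QoR-40 is already collected, state it in the protocol and specify the same analysis.

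The cost is a small amendment, one questionnaire per patient (at most 52) and a few minutes of each patient's time; no extra procedure or staff is needed. The change can apply only to patients not yet operated on. If recruitment is complete, keep the unadjusted comparison, give its 95% CI, and report the missing baseline as a limitation.
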